*** 5. Does your study involve incomplete disclosure or deception?**

☐ Yes ☒ No

*** 6. Data Analysis: Describe the analytical techniques the researcher will use to answer the study questions.**

Descriptive, bivariate and basic multivariate quantitative analyses (pre and post controlling by sociodemographic information). Data from focus groups will be analyzed using a content analysis approach.

*** 7. If there are procedures or methods that require specialized training, describe who (role and qualifications) will be involved and how they will be trained. e.g., cognitive assessments, specialized intervention or technique, blood draws, etc. If not, state not applicable.**

Facilitators will have a social work, case management or other human development or clinical background. Drs. [name] and [name] of the Optimal Aging Institute will train facilitators.

Identifiers

- * **1. Check the identifying information below that you have access to, already have, or will have, and or will receive, even if it is not retained with the research data. This includes any identifiers you may have at any point, even if only temporarily and even if the identifiers are never linked to the study data.**

- ☒ Names
- ☒ Telephone numbers
- ☒ All dates related to the subject (e.g. birth date, admission/discharge date, test date)
- ☐ Geographic subdivision smaller than a State (e.g. address, city, county, precinct, zip and geocode)
- ☐ Fax numbers
- ☒ Electronic mail addresses
- ☐ Social Security numbers
- ☐ Student or Employee ID numbers
- ☐ Device identifiers and serial numbers (e.g., implanted medical device)
- ☐ Certificate or license numbers
- ☐ Biometric identifiers, including finger and voice prints
- ☐ Account numbers (this could be any type of account that is unique to the participant)
- ☐ Health plan beneficiary numbers
- ☒ Full face photographic images and any comparable images
- ☐ Internet protocol (IP) address numbers
- ☐ Medical record numbers
- ☐ Vehicle identifiers and serial numbers (VIN), including license plate numbers
- ☐ Web universal resource locators (URLs)
- ☐ Any other unique identifying number, code or characteristic
- ☐ None of the above

Identifier Details

- * **2. For each of the items checked above, explain why this information will be collected and how it will be used.**

The research team will need the names, ages, phone numbers, and email addresses of participants to contact them regarding the session participation and completion of assessments and focus groups. Ages of the participants is needed by the research team because participants must be at least 45 years of age. Upon completion of data collection all data be de-identified. Only members of the research team identified by the PI will have access to de-identified data. Full face images in the form of video recording of the participants during the program zoom sessions and focus group zoom sessions will be reviewed by members of the research team to identify issues related to program delivery, acceptability and to conduct content analysis for the focus group sessions. These recordings will be store on secured UNCC systems and servers and only members of the research team identified by the PI will have access to these recordings. These recordings will be stored separately from survey data.

- * **2.1 How will these identifiers be stored in relationship to the research data:**

- ☒ with the research data. -- i.e., in the same data set/same file (whether electronic or hardcopy data)
- ☒ separate from the research data. -- i.e. coded with a linkage file stored in a different location. The location must be physically separate, whether it's a physical location (different cabinet, room, etc.) or electronic location (different folder with access restrictions, different network drive, etc.

- * **Provide details about the option you selected above.**

A separate secure dropbox folder will be created for the sessions recordings and the focus group recordings. This will be a different dropbox folder than the one used for assessment or registration data. We acknowledge that video data cannot be separate from all identifiers.

Instructions - In your description be sure to explain the following:

- How will participant identifiers be handled?
- Will data be identifiable or anonymous? Note: Anonymous means that no one, not even the Researcher will know the identity of the participant.
- Describe if and/or how data will be coded. Will a study ID be assigned, a pseudonym, etc?
- Will a master list be used that links participant identity to assigned code/ID/pseudonym?
- How will audio or video recordings be handled?

- * **1. Describe procedures for maintaining privacy of the participant (identity) and the confidentiality of the data you will collect or will receive (e.g., coding, anonymous responses, use of pseudonyms, etc.).**

The data will be de-identified by the research team. Each participant caregiver will be given an ID number that will be used for the entire data available for each participant. Only the PI and Project Coordinator will have access to the Master list linking the participant ID with identifiable data. Video recordings will be stored in a separate Dropbox folder from survey data.

- * **2. Are you collecting sensitive information such as sexual behavior, HIV status, recreational drug use, illegal behaviors, child abuse or physical abuse, immigration status, etc?**

☐ Yes ☒ No

- * **3. If this study is limited to data collection by survey or interview, discuss the potential for deductive disclosure (i.e., directly identifying subjects from a combination of indirect IDs). State "Not Applicable" if this does not apply to this study.**

Personal information will be associated with an ID number. We will use the ID number to link the individual with the data. A master list linking ID numbers to participant information will be stored securely on UNCC systems and servers and accessible only to the PI and the project coordinator via a secure Dropbox folder. Electronic data will be stored on a secure and encrypted network at the University of NC Charlotte campus, with password required for access. Native windows encryption will be used to maintain secure the data. Any hard copy data will be stored in locked cabinets in the office of the principal investigator at [name]

Data reports will not include reference to individual participants. Data will be reported for the aggregate information of all participants. No unique or singular data traceable to a participant will be included.

- * **4. Will any of the groupings or subgroupings used in analysis be small enough to allow individuals to be identified?**

☐ Yes ☒ No

Data Storage

Instructions:

- Please refer to [OneIT Guidelines for Data Handling](#) for Level 2 and/or Level 3 data.
- Consult with your College Data Security Officer as needed.

- * **1. Describe the procedures for storing the data. Including, your plans for disposition of data or human biological specimens that are identifiable in any way (directly or via indirect codes) once the study has ended. Describe how and when linkage codes and/or identifiers will be done destroyed.**

All video recordings recorded via the HIPPA compliant Zoom platform will be stored on secure UNCC servers in a secure and Password protected Dropbox folder. The audio and video files will be kept for three years and then destroyed. Participants who consented to participate in the study will be emailed a link to a password protected Qualtrics survey to complete the pre- and post-assessments. These data will be stored on secure UNCC servers in a secure and password protected Dropbox folder. Only the PI and project coordinator will have access to identifiable data. The security of these electronic data is enhanced by using the UNC encrypted protocol. All video recordings will be destroyed three years following the closure of the project. These recordings will be stored on secure UNCC servers in password protected drobox folders for the duration of the study and up to two years following the closure of the project. All other identifiable data including Master lists and data obtained from Qualtrics surveys will also be destroyed upon closure of the study. These data will be stored on secure UNCC servers in password protected Dropbox folders for the duration of the study and up to two years following the closure of the project.

Information collected from Individuals who do not qualify for the study will be destroy and no record will be saved.

Data Transfer and Sharing

Instructions:

- Please refer to [OneIT Guidelines for Data Handling](#) for Level 2 and/or Level 3 data.
- Consult with your College Data Security Officer as needed.

- * **1. Describe how data will be shared among research team (i.e., personnel listed on this application).**

be stored on secure UNCC servers in a secure and Password protected Dropbox folder. Participants who consented to participate in the study will be emailed a link to a password protected. Qualtrics survey to complete the pre- and post-assessments. These data will be stored on secure UNCC servers in a secure and Password protected Dropbox folder. Only the PI and project coordinator will have access to identifiable data. The security of these electronic data is enhanced by using the UNC encrypted protocol.

* **2. Will identifiable data be shared with individuals outside of the research team?**

☐ Yes ☒ No

Benefits

Instructions

- Do not cite monetary payment or other compensation as a benefit.

* **1. Describe the benefit to society based on scientific knowledge to be gained.**

This study will contribute to the Latino community since currently there are no psychoeducational program for Latino caregivers of PLVD in Spanish.

* **2. Describe the direct benefit to individual participants in this study. If there are no direct benefits to the individual participant, say so here and in the consent form if there is a consent form.**

Participants attending the Cuidando Juntos program may experience potential benefits including decrease levels of depression, stress, and an increase of social connectedness and social support. These mental health and skill care building benefits are possible but not guaranteed.

Risks

Instructions

- For each of the following categories of risk, describe the potential risk and what will be done to minimize the risks.
 - Psychological risk (e.g., emotional distress or embarrassment)
 - Social risk (e.g., loss of reputation/standing, harms to a larger group or community, etc.)
 - Economic risk (e.g., loss of income, loss of employment or insurability, loss of professional standing, etc.)
 - Legal risk (e.g., disclosure of illegal activity, disclosure of negligence, etc.)
 - Physical risk (e.g., medication side effects, pain, discomfort, injury, etc.)
- Where possible, describe the likelihood of the risks occurring, using the following terms:
 - Very Common (approximate incidence >50%)
 - Common (approximate incidence > 25%)
 - Likely (approximate incidence 10-25%)
 - Infrequent (approximate incidence 1-10%)
 - Rare (approximate incidence <1%)

1. Describe any potential risks - physical, psychological, economic, social, legal, discomforts, hazards, or other - and assess the likelihood and seriousness for each risk described.

We anticipate no psycho-social or economic harm, legal jeopardy, or risk of pain or injury to the participants in this study. There is no medication involved in this study. However, participants may experience some embarrassment or emotional distress when confronting issues inherent in providing care to family members with dementia as one on the main goals of the intervention is to help caregivers identify and better manage difficult behaviors exhibited by the care recipient as well as the caregiver's response to such behaviors and stressful situations.

2. Describe the procedures for protecting against or minimizing any potential risks.

Facilitators will provide information to caregivers about available counselling services in the community. We do not expect any breach of confidentiality, but in the case that happens we will follow a protocol where the facilitator or Research Assistant is instructed to report immediately to the Principal Investigator. A report will be kept of any potential events. If needed professional services will be recommended for participants. The data from the assessment interviews and the program sessions will be kept under the supervision of the Principal investigator and subject to de-identification.

Data and Safety Monitoring

* **1. Are there criteria that will be used to withdraw an INDIVIDUAL PARTICIPANT from this study or halt the research intervention. E.g., abnormal lab tests, allergic reactions, failure or inability to comply with study procedures, etc?**

☐ Yes ☒ No

* **2. Are there criteria that will be used to stop the ENTIRE STUDY prematurely? E.g., safety, efficacy, unexpected adverse events, large number of unanticipated events, inability to recruit sufficient number of participants, etc.**

☐ Yes ☒ No

* **3. Will this study involve a data and safety monitoring board or committee? A DSMB monitors the progress of the research and safety of participants.**

☐ Yes ☒ No

Instructions

- Complete the questions below that pertain to the use of existing records/data or human biological specimens.
- Existing data refers to data you will receive, obtain, or access from a source other than your study participant.
- Data obtained from secondary sources that was not collected for the purposes of your study.

Data Sources

* Will you use or obtain any records, data, or human biological specimens that have already been collected?

☐ Yes ☒ No

Instructions

- Please refer to Financial Services Human Subjects Payments, How to Pay guide. Link available in the Resource Bar.

Incentives and Costs

- * 1. Are there incentives (monetary or non-monetary) for participants to participate or are you reimbursing participants for study-related costs (e.g., travel, parking, hotel accommodations or childcare)?
☐ Yes ☒ No
- * 2. Will there be any financial costs that participants will incur related to participation in the study?
☐ Yes ☒ No

Instructions

- Use this page to upload any supporting documents that are relevant to your protocol.
- Before uploading, carefully review the e-file title of each document. The e-file should clearly identify the content of the document (e.g., Social Media Recruitment, Interview Questions, Parental Consent, etc.).
- Each table contains different document types. To add an attachment click the "Add" button in the appropriate table. If you can't find the specific document type you need, each table has an "other" option that you may choose.
- If you have a document that doesn't "fit" one of the table categories, use the "Other" table and select "other" as the document type.
- After clicking Add and selecting a Document Type, click the upload icon (upwards arrow). This opens a pop-up box for you to search and select your document.
- If you successfully uploaded the document, the document name and date and time of upload will appear next to the upload icon in the table.

Attachments

Master Protocols, Grants, Proposals

Document Type	Upload protocols, grants, proposals	
Grant Application	OtherClinicalTrialRelatedAttachments_Project9TLC.pdf	21-Oct-2023 12:08:18 PM
Other Study Protocol	SESSION by SESSION OUTLINE Draft for CAB to Review 10_18_23.docx	21-Oct-2023 12:19:36 PM

Data Collection Materials

Document Type	Upload Data Collection Materials	
Online Survey	Project 9 Measures.docx	21-Oct-2023 12:10:23 PM

External IRB/Multi-Site Studies

Document Type	Upload External IRB/Multi-Site Studies	
---------------	--	--

Sponsor-Related Materials (monitoring, regulatory)

Document Type	Upload Sponsor-Related Materials	
---------------	----------------------------------	--

Consent Related Materials

Document Type	Upload Consent Materials	
	Program Consent Form Cuidando Juntos Consent form November 2023.docx	15-Nov-2023 01:37:42 PM

Recruitment Materials

Document Type	Upload Recruitment Materials	
Flyer	cuidando juntos flyer (1).docx	04-Nov-2023 11:46:33 AM

Other Approvals and Agreements

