All potential participants must complete a registration/screening questionnaire administered via a link to the Qualtrics survey on the registration website to indicate their interest in and qualifications to participate in the study. Participants will provide basic demographic information including names, age, race/ethnicity, languages spoken, contact information including email addresses, phone numbers, location, general availability, and the nature of the care provided to the family member with dementia. The registration/ screening questionnaire will also contain the Perceived Stress Scale [PSS-10] and the the Modified Caregiver Strain Index [MCSI] as participants **must experience elevated caregiving stress (as measured by a score of = 11 on the 10 item Perceived Stress Scale [PSS10] and/or a score of 5 or greater on the Modified Caregiver Strain Index [MCSI])**.

Members of the research team will review the registration information to determine eligibility as all participants must be 45 years of age or older and provide care to a family member or friend with dementia and must experience elevated caregiving stress (as measured by a score of = 11 on the 10 item Perceived Stress Scale [PSS10] and/or a score of 5 or greater on the Modified Caregiver Strain Index [MCSI]). Participants who qualify will be contacted with instructions (via email or phone: preference to be indicated by potential participants on the initial registration/screening questionnaire) to complete the informed consent, indicate again their availability for participation in the group sessions, and complete the first assessment. In sum, once the potential participant is at the registration website, they will complete a registration/screening survey if they wish to be considered for participation. Then, qualifying participants will be contacted by a member of the research team and will be provided with further instructions regarding completion of the informed consent form. All participants who qualify will be sent a link to a Qualtrics survey containing a full consent form minus the signature line as well as a pdf document of the informed consent form minus the signature line for their records. Participants will indicate their consent and receipt of this consent form by indicating their informed consent on the Qualtrics survey. Participants who do not consent to participate will not be contacted further by the research team and all identifying information will be deleted from the records.

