
Assessment and Cuidando Juntos Sessions:

Once informed consent is obtained, participants will be contacted regarding completion of the first assessment survey (pre-assessment). Once the consent form and first survey is completed each participant will be assigned to a group led by one of the trained facilitators based on the indicated availability. Once assigned to a group, participants will be emailed their zoom invitation from the facilitator. After completing the Cuidando Juntos program, participants will be emailed a link to a post assessment Qualtrics survey. Participants will also be required to indicate their consent on each electronic survey (pre and post) prior to accessing any survey questions. Participants who do not indicate their agreement to proceed with each electronic survey will not be directed to respond to any survey questions and will also be asked if they would like to withdraw from the study and receive no further contact from the research team. Participants will also be asked to participate in a focus group and answer semi-structured interview questions after completing the Cuidando Juntos program. Participants will indicate their consent to participate in the semi-structured interview on the initial consent form and will also be emailed a link to an electronic survey administered via Qualtrics and will be required to indicate their consent to participate in the semi-structured interview focus group prior to being emailed the link to the Zoom meeting. Participants who do not indicate their agreement to participate in the focus group will also be asked if they would like to withdraw from the study and receive no further contact from the research team. Participants who indicate they would like to completely withdraw will no longer be contacted by members of the research team. Participants can choose to withdraw from the study at any time.

Confidentiality and Program Access:

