We will assess caregivers approximately one week prior to the training one week after completing the program. These measures are standard in the caregiving literature, and focus on both the positive and potential negative aspects of caregiving. At each occasion, they would require approximately an hour to complete. In addition to these assessments, caregivers will attend 6 weekly sessions to complete the program. Participants will also answer semi-structure interview questions as part of focus group discussions after completing the six week sessions.

The estimated duration of participation is approximately 2 months.

After qualifying participants are consented they will be assigned to participate in the "Cuidando Juntos" program group. Once assigned, participants will complete a pre assessment survey approximately one week before beginning the program. The pre-assessment survey will be completed virtually using Qualtrics and will take approximately 40 minutes to complete. Participants will then complete the six weekly "Cuidando Juntos" program sessions, each lasting two hours. One week after completion of the sessions participants will complete a post assessment survey virtually using Qualtrics, which will take approximately 40 minutes to complete. Between one and two weeks after completing the program sessions, all participants in the program group will be invited to participate in a virtual focus group via HIPAA zoom platform. Participants will be ask to respond to semi-structured questions about the program during the focus group. The group will be lead by a bilingual/bicultural member of the research team. The focus group will last two hours. Total participation for the duration of the study will be approximately ten week for participants.

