a. Metrics to assess acceptability of the adapted Caregiver TLC program at conclusion of the early stage trials studies: - Number of “hits” to website and program materials; - % completed action plans; - 6 point self-report Likert scales for: program satisfaction; new skills learned; usefulness of skills; helpfulness of skills; likelihood of using skills in future. b. To measure the mechanism of social connectedness, we will administer the following before & after intervention. - Lubben Social Network Scale-6, Spanish translation (culturally adapted as well as translated into Spanish; Vilar-Compte, Vargas-Bustamante & Lubben, 2018). It is a measure of social isolation (by identifying and counting people in the network including family/ friends and identifying who to talk with about private matters”); -To measure Loneliness we will use the UCLA Loneliness Scale (full version, 20 items). Feelings of loneliness maybe inversely related to feeling connected and supported by family and friends (Russell, Peplau & Cutrona, 1980). c) Clinical outcomes: to be collected before & after early intervention trials: - Perceived Stress Scale, 10 item version (Cohen et al., 1983), available in Spanish; - Zarit Caregiver Burden 6-item version (Higginson, et al, 2010), translated into Spanish (Martin-Carrasco et al., 2010), and PHQ-9 to assess depressive symptoms (Kroenke & Spitzer, 2002; available in Spanish). d) We also assess for the role of Familism and Acculturation using the scales developed by Marin, Sabogal et al. (1987). Highly acculturated Latino dementia caregivers are likely to more extensively use support services outside the home (and rely less on family) to care for PLWD.

7. Future Directions/ Next Steps: This work is regarded as preliminary to development of an Stage II efficacy trial grant proposal to submit in 2024 which will test the acceptability of the culturally adapted Caregiver TLC in a rigorous controlled trial. We aim to develop an RO1 level multi-site Stage III-IV trial to test the efficacy of this virtual adapted Caregiver TLC program with Latino caregivers in different parts of the US.

Background Questions:

Please answer the questions below in regard to your project. Not to exceed 1 page.

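### The visible plan collects the PHQ-9 remotely before and after the program, but ties neither support measure to its results and assigns no one to review answers on arrival

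*Combined protocol and SAP*

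**What the plan says.** The PHQ-9 is named in two places: the pilot application's Analytic Plans (clinical outcomes) and Appendix 3, Measures, part D. In both it is an outcome taken before and after the intervention, "PHQ-9 to assess depressive symptoms", with no rule for handling an answer.

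Both assessments are remote. Under Duration of participation: "The pre-assessment survey will be completed virtually using Qualtrics and will take approximately 40 minutes to complete", about one week before the program starts; then "One week after completion of the sessions participants will complete a post assessment survey virtually using Qualtrics".

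Risks, question 2, asks how risks will be minimized. Two supports are given: "Facilitators will provide information to caregivers about available counselling services in the community" and "If needed professional services will be recommended for participants". The same answer has a duty to report immediately to the PI, but for a breach of confidentiality.

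The stated review of individual answers for a decision is under Registration and Consent: "Members of the research team will review the registration information to determine eligibility". The instruments there are the PSS-10 and the MCSI. Under Data and Safety Monitoring, individual withdrawal criteria, study stopping criteria and a monitoring board are all answered No.

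**The concern.** A depression questionnaire can show that a respondent needs help. The study enrols caregivers selected for elevated stress, and its own rationale says that Latino caregivers report more depression than other groups, so some high PHQ-9 answers are foreseeable. The visible eligibility criteria exclude no one for severe depression.

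The survey is filled in online with no staff member present. If no one is asked to look at the answer, the team could hold the information that should prompt its own conditional recommendation and not act on it. At stake is the protection of participants. The validity of the pre-post comparison is not in question.

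**Working it through.** The check is mainly a reading of the text, with two small sums.

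**1. Is either support tied to the PHQ-9?** Counselling information comes from facilitators and carries no score, item or time limit. The professional-services recommendation depends on need, but names no one to judge need, no trigger and no timing. Neither mentions the PHQ-9.

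**2. Is anyone assigned to review PHQ-9 answers on arrival?** The candidate statements are:

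| Place | What it provides | PHQ-9 review? |
|---|---|---|
| Registration and Consent | Eligibility review of registration data | No |
| Assessment and Session Protocols | Mailing address taken from the Time 1 survey, so the coordinator can post materials | Individual records are used, but not their PHQ-9 answers |
| Confidentiality and Program Access | Research-team access to assessment data | Access only |
| Data management (confidentiality, storage) | PI and coordinator hold the master list and identifiable data | Access only |
| Risks, question 2 | PI supervision of data; a report kept of events | Custody and record-keeping |

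None assigns the task.

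**3. Does other contact fill the gap?**
- Facilitators are trained and come from social work, case management or related human-development and clinical fields (Methods and Procedures, question 7). They lead six weekly two-hour sessions.
- Contact can begin before session 1: "Once assigned to a group, participants will be emailed their zoom invitation from the facilitator".
- Session 5 covers mental health, and session 6 covers where to find support.
- One to two weeks after the sessions, "all participants in the program group will be invited to participate in a virtual focus group via HIPAA zoom platform".

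This is real mitigation. But nothing in the visible text passes PHQ-9 answers to facilitators, no program session is scheduled after Time 2, and the focus group is an invitation to discuss the program. All of it reaches caregivers whatever they answered.

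**4. How many responses?** Surveys per person = 2.
- Pilot application, Study Design: 20 × 2 = 40.
- IRB application, Number of Participants: 30 × 2 = 60, if everyone completes both.

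**5. How long might a Time 1 answer wait?** The plan does not say. Time 1 to Time 2 is 1 week before session 1, plus 5 weeks from session 1 to session 6, plus 1 week after: 1 + 5 + 1 = 7 weeks. This is the minimum wait only on the assumption that answers are first read for the pre-post comparison.

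The documents give no PHQ-9 cut-off and no expected rate of serious responses, so no probability is computed.

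**The case against.** The strongest reply is that this is an initial IRB application. Survey content was still being developed, surveys and translated consents were to be added to the IRB, and no participant would be contacted before then. The text of the program consent form is not available to this review. A distress procedure could be in either place. This stands: the point is limited to the visible text and is partly a request to confirm. It does not remove the point, because the PHQ-9 was already in the submitted measures and the answer on risk was already written.

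A second reply is that Time 1 records are handled early. Addresses are taken from them, and group assignment waits for the first survey to be completed. This also stands. A reader might infer that a serious answer would lie unread until analysis, or for seven weeks. No passage says so, and the early use of these records weakens that reading. Taking an address from a record is still not a review of its depression answers.

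A third reply is that qualified facilitators in weekly contact make the conditional recommendation workable. In part they do, for need that shows itself in sessions. They cannot act on an answer that they are not given.

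Finally, acting on answers could alter the Time 2 score in an uncontrolled design. That is correct, and it is a reason to record referrals.

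**Conclusion.** The point holds as an omission in the visible text, and the remedy is a cheap improvement. Its extent is 40 to 60 PHQ-9 responses with no stated review on arrival; that counts surveys and does not measure risk. Seven weeks is an assumption about one possible delay.

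Two stronger inferences should not be drawn. The documents do not show that the study has no safeguards: counselling information, a conditional recommendation and trained facilitators are all present. Nor do they show that no procedure exists anywhere, since the consent text and final surveys cannot be seen. No harm to any participant is shown, and nothing here contradicts another part of the plan.

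Confidence is medium, because the conclusion rests on the visible text being complete on this point.

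**What to change.** In the answer to Risks, question 2:

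- Assign the project coordinator or the PI, who hold the master list, to check each PHQ-9 response on submission at both time points, for example by a Qualtrics notification.
- Fix the trigger in the IRB submission already planned before participant contact. An explicit rule means that the check itself needs no clinical judgement; the visible text states no clinical qualification for the coordinator.
- When the trigger is met, the PI makes the existing professional-services recommendation promptly, in Spanish where needed.
- Record every referral made after Time 1 and report it with the PHQ-9 change, because in this single-arm design a referral could affect Time 2.
- If the consent form or final surveys already contain such a procedure, cross-reference it here.

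The cost is low: one or two sentences of protocol text, a survey setting, an agreed trigger, a Spanish-language referral list, matching consent wording, and staff attention to 40 to 60 short responses. The analytic cost is that PHQ-9 change may partly reflect referrals. Recording them makes this visible but does not remove it.
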